2.2 Background & Rationale, Significance of Selected Topic & Preliminary Data	
The annual incidence of foot ulcers among diabetics has been estimated at between 6% to 11.5%, and 10 to 15% of those with diabetes will have at least one foot ulcer during their lifetime. The majority (upwards of 60%) of these diabetic ulcers become infected. Treatment of these complicated diabetic wound infections primarily involve surgical intervention, topical antiseptics, and systemic antibiotic therapy. However, despite advances in these areas, outcomes from such infections remain poor and often lead to limb amputation in 15% to 20% of participants within 5 years.
 
Gram-positive organisms, particularly Staphylococcus aureus, are the main pathogens found in diabetic wound infections. As antibiotic resistance rates have risen, methicillin-resistant S. aureus (MRSA) has also become more frequent in acute bacterial skin and skin structure infections (ABSSSI). Additionally, diabetic wound infections caused by MRSA are associated with worse outcomes compared with other pathogens. As a result, antibiotics targeting MRSA are often prescribed for the treatment of diabetic wound infections either as monotherapy, or in combination with other antibiotics to cover Gram-negative and anaerobic bacteria that also may be present.
 
Tedizolid (Sivextro®, Cubist Pharmaceuticals Inc., Lexington, MA), the active moiety of the prodrug tedizolid phosphate, is an oxazolidinone antibiotic approved by the FDA for the treatment of ABSSSI caused by S. aureus (including MRSA), Streptococcus pyogenes, Streptococcus agalactiae, and Enterococcus faecalis. A 6-day course of tedizolid was well-tolerated and non-inferior to 10-day course of linezolid in Phase II and Phase III clinical trials of ABSSSI.
 
The pharmacokinetic profile of tedizolid has been described in numerous patient populations. However, the penetration into tissue during an active infection has yet to be elucidated. The most accurate method to calculate overall penetration is to evaluate the entire drug exposure, or AUC, in the tissue of interest and compare this with the overall AUC in blood. In the setting of clinical infection, our group has successfully applied a technique called in vivo microdialysis to assess the interstitial (i.e., extracellular) concentration profile of antimicrobials in comparison to their systemic exposures. This approach involves placing a probe with a semi-permeable membrane at the tip into tissue and constantly perfusing the probe with a physiologic solution via a pump; this approach allows for the continuous collection of extracellular fluid from the tissue and enables assessment of drug concentration over a specified time period (i.e., the entire dosing interval). Using this methodology, the penetration of a single 600 mg oral dose of tedizolid into muscle and subcutaneous adipose tissue of the thigh was assessed in 12 healthy volunteers. Tedizolid demonstrated an <math>AUC_{\text{tissue}}/AUC_{\text{plasma}}</math> ratio of 1.1 and 1.2 for adipose tissue and muscle, respectively, indicating excellent tissue penetration for the oral route of the drug administration into healthy volunteers. Although these data are promising, the

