2.6 Study Duration	
IRB Submissions and Approval 2 months
 
Enrollment and Sampling of 10 Patients 6-12 months
 
Enrollment and Sampling of 6 Healthy Volunteers 4 months
 
Tedizolid HPLC 1 month
 
Pharmacokinetic Analysis 1 month
 
Final Report 2 months

2.7 Statistical Analysis and Sample Size Justification	
2.7.1 Data Validation and Analysis
 
The Principal Investigator will be responsible for the review, validation, and analysis of these data as collected and recorded by the study staff.
 
2.7.2 Primary Endpoint:
 
The primary endpoints of the study are to assess the penetration of tedizolid into infected skin tissue and compare it to the penetration into healthy skin tissue, as well as to assess the pharmacokinetics of tedizolid in plasma of both study populations.

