	
2.7.2.1 Primary Endpoint Definition:
 
Percentage of tissue penetration of tedizolid will be defined based on the AUC in plasma and tissue and will be calculated as: <math>AUC_{\text{tissue}} / \text{free}AUC_{\text{plasma}} \times 100</math>. Plasma pharmacokinetic parameters that will be estimated including: <math>AUC_{0-24 \text{ (plasma)}}</math>, elimination rate constant (<math>K_e</math>), half-life (<math>t_{1/2}</math>), total plasma clearance (<math>CL_T</math>), and Volume of distribution (<math>V_d</math>).
 
2.7.3 Statistical Analysis
 
Non-compartmental pharmacokinetic analyses for tedizolid will be conducted using Phoenix (version 6.3, Pharsight Corporation, Mountain View, CA). Pharmacokinetic parameters for plasma will be determined using each individual's plasma concentration-time profile. The maximum concentration (<math>C_{\text{max}}</math>) for each participant will be estimated by visual inspection of the concentration-time profiles. The log-linear trapezoidal method will be used to determine <math>AUC_{0-24 \text{ (plasma)}}</math> for each participant. The elimination rate constant (<math>K_e</math>) will be estimated by the slope of the terminal portion of the concentration-time profile; half-life (<math>t_{1/2}</math>) will be calculated by <math>0.693/K_e</math>. Total plasma clearance (<math>CL_T</math>) will be calculated by Dose/<math>AUC_{0-24 \text{ (plasma)}}</math>. Volume of distribution (<math>V_d</math>) will be calculated by <math>CL_T/K_e</math>.
 
All microdialysis concentrations will be corrected for recovery before pharmacokinetic analysis as follows: <math>\text{Concentration}_{\text{tissue}} = 100 \times (\text{Concentration}_{\text{sample}} / \% \text{ in vivo recovery})</math>. The <math>AUC_{0-24 \text{ (tissue)}}</math> will be assessed by the log-linear trapezoidal rule. Percentage of penetration into tissue will be calculated as follows: <math>AUC_{\text{tissue}} / \text{free}AUC_{\text{plasma}} \times 100</math>.
 
A Student's t-test will be used to compare the penetration ratio and pharmacokinetics of tedizolid between study and control groups.
 
2.7.4 Sample Size Determination
 
Ten patients with diabetic foot infection (Study Group) and six healthy volunteers (Control Group) are to be enrolled in the study.
 
This is primarily a descriptive, controlled study to observe the exposure and penetration ratio of tedizolid into the interstitial fluid of infected tissue of diabetic patients and compare it to that of healthy volunteers. In similar study designs, 10 study patients were sufficient to describe the central tendency of these penetration estimates and some confidence of dispersion. Given reduced variability in healthy participants, 6 volunteers will be utilized.

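### Section 2.7.3 compares 10 patients with 6 controls by a Student's t-test alone; a geometric mean ratio with 95% CI from Welch's test on log values is a cheap improvement

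*Combined protocol and SAP*

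**What the plan says.** Section 2.7.2 makes penetration into infected versus healthy tissue a primary endpoint, "as well as to assess the pharmacokinetics of tedizolid in plasma of both study populations". Section 2.7.2.1 defines penetration as tissue AUC over free plasma AUC, times 100, and lists the plasma parameters.

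Section 2.7.3 sets out how each person's parameters are derived: clearance is dose divided by the 24-hour plasma AUC, and half-life is 0.693 divided by Ke. The between-group analysis is then one clause, a Student's t "test will be used to compare the penetration ratio and pharmacokinetics of tedizolid between study and control groups". The log-linear rule named there concerns AUC integration, not the scale of the comparison. No alpha, sidedness, group summary, difference or ratio, or confidence interval is stated.

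Section 2.7.4 says: "Ten patients with diabetic foot infection (Study Group) and six healthy volunteers (Control Group) are to be enrolled in the study". It adds: "This is primarily a descriptive, controlled study to observe the exposure and penetration ratio of tedizolid into the interstitial fluid". The patient number rests on precedent, in that "10 study patients were sufficient to describe the central tendency of these penetration estimates and some confidence of dispersion". The control number rests on a variance premise: "Given reduced variability in healthy participants, 6 volunteers will be utilized". No SD or CV is given.

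**The concern.** A study whose stated aim is description should commit to an estimate and its uncertainty. A t-test sentence alone does not, and with 10 against 6 the range of ratios compatible with the data will be wide whatever the p-value.

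Two choices are left open.

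- **Variance.** In its usual meaning Student's test pools the variances, while 2.7.4 expects the smaller group to vary less.
- **Scale.** The endpoint is a positive ratio, and two pairs of plasma parameters (AUC and clearance, Ke and half-life) are reciprocals up to a constant. On raw values the two members of a pair can give different test results from the same data.

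At stake are some power, the consistency of the plasma results, and the risk that a non-significant result is taken to mean equal penetration.

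**Working it through.** **Inputs.** From 2.7.4: n = 10 patients and 6 controls. The plan's sample size cannot be reproduced, because no alpha, power, effect size, SD or precision target is given. Assumed here: two-sided 5%, log-normal data with log-SD = √ln(1+CV²), CVs of 20 to 40% (written patient/control), and true ratios of 0.7, 1.0 and 1.4. Size, power and interval width come from simulation.

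**1. Effect of pooling, by hand.** Let the control SD be 1.

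- Patient SD 2: pooled variance = (9×4 + 5×1)/14 = 2.929. Pooled SE² = 2.929×(1/10 + 1/6) = 0.781. True SE² = 4/10 + 1/6 = 0.567. The SE is too large by √(0.781/0.567) = 1.174, so the test is conservative.
- Patient SD 0.5: pooled variance = (9×0.25 + 5×1)/14 = 0.518. Pooled SE² = 0.138, against a true 0.192. The SE ratio is 0.849, so the test is anti-conservative.

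Simulated size on normal data, by patient:control SD ratio:

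| SD ratio | 0.5 | 1 | 1.5 | 2 |
|---|---|---|---|---|
| Student | 9.9% | 5.0% | 3.4% | 2.8% |
| Welch | 5.3% | 4.9% | 4.8% | 4.8% |

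On raw log-normal values at CVs from 30/25% to 40/20%, Student's size is about 2.6 to 4.0%.

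**2. Power: Student on raw values vs Welch on logs.**

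| CV | ratio 0.7 | ratio 1.4 |
|---|---|---|
| 30/25% | 64 vs 66% | 54 vs 61% |
| 30/20% | 69 vs 76% | 61 vs 71% |
| 40/30% | 43 vs 48% | 34 vs 44% |
| 40/20% | 47 vs 61% | 41 vs 56% |

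If variances are equal the sign turns at ratio 0.7: 60 vs 56% at 30/30% and 40 vs 37% at 40/40%.

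**3. Width of the interval.** At 40/30% the log-SDs are 0.385 and 0.294, so SE = √(0.385²/10 + 0.294²/6) = 0.171. The Welch degrees of freedom are about 13, with t = 2.160, and the CI factor is exp(2.160×0.171) ≈ 1.45. The simulated median is 1.44, so an observed ratio of 1.0 would carry about 0.70 to 1.44. Simulated medians elsewhere: 1.24 (20/20%), 1.34 (30/25%), 1.36 (40/20%), 1.38 (30/30%) and 1.53 (40/40%). Coverage is 95.0 to 95.2%.

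**4. Reciprocal parameters (plasma only).** log CL = log Dose − log AUC, so on logs the two tests are identical apart from sign; the same holds for Ke and half-life. On raw values with Student's test, AUC and clearance differ on significance in about 4 to 13% of datasets at ratios 0.7 or 1.4, and in 1 to 3% under the null. Welch on raw values does not cure this: 14 to 17% at 30/30, 30/25, 40/30 and 40/20%. Volume of distribution is different, since log Vd = constant − log AUC − log Ke. With AUC and Ke independent, CV 40/30% and both true ratios 0.8, Vd is significant with neither AUC nor Ke significant in 9.6% of datasets. It needs its own comparison.

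**5. Missed differences.** With the planned test on raw values, a true ratio of 0.7 is missed about 10% of the time at CV 20/20% and about 60% at 40/40%.

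**The case against.** The best defence is that nothing here is broken. A t-test implies a mean difference from which an interval follows, and 2.1.1 and 2.7.4 already commit to describing the profile. Pooling matters little for interval width in several scenarios: median CI factors on logs, Student vs Welch, are 1.35 vs 1.34 at 30/25% and 1.37 vs 1.38 at 30/30%, with a clear gap only at 40/20% (1.43 vs 1.36). Inflated size needs controls to vary more than patients, contrary to 2.7.4. The reciprocal problem does not reach the penetration endpoint, which has no listed reciprocal, and testing one member of each pair would also remove it. The documents nowhere claim equal penetration.

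Most of this stands, and it limits the point. Most of the gain comes from committing to an estimate with a CI; Welch and logs add less. What remains is that the plan writes down neither an estimate with CI nor a scale. Under its own variance premise, the proposed analysis also has more power in both directions in all four scenarios of step 2.

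A reader might also take the background's "ratio of 1.1 and 1.2 for adipose tissue and muscle, respectively, indicating excellent tissue penetration" as support for a between-group ratio. It is not. Those figures are tissue/plasma ratios in healthy volunteers, the kind of quantity 2.7.2.1 already defines, and they say nothing about patients relative to controls.

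**Conclusion.** The point holds as a worthwhile, low-cost improvement, not as an error that threatens validity. Under the plan's premise of less variable controls, Student's test on raw values is conservative and, across the four assumed CV pairs, gives up about 2 to 14 points of power at ratio 0.7 (66−64 to 61−47) and about 7 to 15 at ratio 1.4 (61−54 to 56−41). The ratio will be estimated only to within about ×/÷ 1.24 to 1.53, so the interval should be reported.

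Three stronger readings are not supported.

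- That the test contradicts 2.7.4 or is invalid: no SD or CV is given, so this is under-specification.
- That the study would miss a 30% lower penetration at some one fixed rate: the documents give no CV, and the honest range is about 10 to 60%.
- That logs raise power in general. Welch on raw vs log values gives 47 vs 56% at ratio 0.7 but 55 vs 52% at ratio 1.4 (CV 30/30%), so the effect of scale changes sign with direction.

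Confidence is high on what 2.7.3 leaves unstated. The sizes depend on the assumed CVs and the two-sided 5% level.

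**What to change.** Replace the t-test sentence in 2.7.3 with:

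> The penetration ratio and plasma PK parameters will be summarised by group as geometric mean and CV%, and compared on the log scale with Welch's two-sided t-test, reported as the patient/control geometric mean ratio with 95% CI; CL_T and half-life carry the same test result as AUC and Ke. A non-significant difference will not be read as equal penetration.

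Volume of distribution keeps its own comparison, and the parameter list in 2.7.2.1 is unchanged. The last clause is a precaution.

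The cost is this rewording, with no new participants or samples. Phoenix is named only for the non-compartmental analysis, so the software for the test should be named too. There are two downsides. About 2 to 4 points of power are lost at ratio 0.7 if variances are equal. The target also becomes geometric rather than arithmetic means: when arithmetic means are equal, Welch on logs rejects 4.9% (30/25%), 5.1% (40/30%) and 6.2% (40/20%) of the time.

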2.8 Specific Drug Supply Requirements	
Tedizolid phosphate 200 mg tablets will be provided by Merck, Inc. as an open label supply.

2.9 Adverse Experience Reporting	
Participants will be monitored for any sign or symptom of adverse events throughout the course of the study. Unanticipated, life-threatening or fatal adverse events will be reported to the IRB, the manufacturer, and the Food and Drug Administration according to federal guidelines. All adverse events requiring medical attention will be treated by the study physician and will be recorded by the investigator.
 
2.9.1 Definitions
 
For the purpose of this study, an adverse event will be defined as any pathologic or unintended change in the structure (signs), function (symptoms), or chemistry (laboratory values) of the body associated with the use of the study drug, whether or

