	
not considered drug related, and will be categorized as one of the following:
 
 
• MILD – present, but easily tolerated
 
• MODERATE – discomfort that interferes with usual activities
 
• SEVERE – incapacitating, inability to work or do usual activities
 
 
A serious adverse event will be defined as any of the above which results in death or is immediately life-threatening, requires in-participant hospitalization, or is an important medical event that may jeopardize the participant or require medical intervention to prevent one of the previously mentioned outcomes.
 
2.9.2 Relationship to Study Medication
 
Relationship of the adverse event to the study medication (i.e., causality) will be evaluated according to the investigator's opinion, as one of the following:
 
 
• Concurrent condition – unrelated to study drug
 
• REMOTE adverse drug event – little or no temporal relationship to study drug
 
• POSSIBLE adverse drug event – temporal relationship to study drug
 
• PROBABLE adverse drug event – commonly associated with study drug
 
• DEFINITE adverse drug event – reappeared on re-challenge of study drug
 
 
2.9.3 Expectedness of Adverse Event
 
As AEs are expected with the study medication, patients will be closely monitored throughout the study for any AE occurrence and will be managed accordingly by the study physician. All AEs will be recorded by the investigator as described in Section 2.9.4 below.
 
2.9.4 Recording and Reporting an Adverse Event
 
All adverse events requiring medical attention will be recorded by the investigator as such: categorization by severity (mild, moderate, or severe), established time frame (start and stop time), complete description of event, all interventions (medical and pharmacological), and causality.
 
2.9.5 Recording and Reporting a Serious Adverse Event (SAE)
 
All SAEs will be reported to the Institutional Review Board, sponsor, and the Food and Drug Administration according to Federal guidelines. A serious adverse event will be defined as any adverse event that results in death, is immediately life-threatening, requires or prolongs hospitalization, or is an important medical event that may jeopardize the participant or may require medical intervention to prevent one of the previously mentioned outcomes.

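### Section 2.9.3 has all adverse events recorded, but the recording rule it points to in 2.9.4, and the opening of 2.9, name those requiring medical attention (minor internal inconsistency)

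*Combined protocol and SAP*

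**What the plan says.** Four places in section 2.9 bear on which adverse events are written down.

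- **2.9, opening paragraph:** "All adverse events requiring medical attention will be treated by the study physician and will be recorded by the investigator". The same paragraph provides for detection: "Participants will be monitored for any sign or symptom of adverse events throughout the course of the study".
- **2.9.1, definition:** an adverse event is "any pathologic or unintended change in the structure (signs), function (symptoms), or chemistry (laboratory values) of the body". The sentence goes on to tie the change to use of the study drug, irrespective of whether the drug is thought to be the cause. The lowest severity grade is defined as "present, but easily tolerated".
- **2.9.3:** "All AEs will be recorded by the investigator as described in Section 2.9.4 below". It also says that "patients will be closely monitored throughout the study for any AE occurrence".
- **2.9.4:** "All adverse events requiring medical attention will be recorded by the investigator as such". A list of fields follows, including "categorization by severity (mild, moderate, or severe".

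Serious adverse events are defined twice. The hospitalization criterion in 2.9.1 covers an event that makes admission necessary. The one in 2.9.5 also covers an event that lengthens a stay.

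Section 2.1.2 gives one secondary objective, the description of safety and tolerability in both groups. Section 2.7 sets out no analysis of adverse events.

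**The concern.** Section 2.9.3 sets a universal scope and sends the reader to 2.9.4 for the method. Section 2.9.4 then begins by naming a subset. The qualifier also stands in the opening paragraph of 2.9, so it is less likely to be a single slip. The protocol does not define what counts as requiring medical attention, so staff would have to judge it case by case.

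What is at stake is the tolerability description. With no adverse event analysis planned in 2.7, that description rests on what is recorded under 2.9. The events in doubt are mild symptoms that nobody treats, and these are part of what a tolerability description is meant to show. If the onset, end and causality of such an event are not noted at the time, they may be hard to reconstruct later.

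**Working it through.** No figure in the plan bears on this point and no arithmetic applies. The check is to take four kinds of event through each section as worded.

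| Event | Adverse event under 2.9.1? | Recorded under 2.9.3? | Named for recording in 2.9 and 2.9.4? |
|---|---|---|---|
| Mild symptom that receives medical attention | Yes | Yes | Yes |
| Mild symptom, easily tolerated and untreated | Yes | Yes | No |
| Unintended laboratory change needing no attention | Yes | Yes | No |
| Moderate or severe event requiring attention | Yes | Yes | Yes |

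1. **Rows 1 and 4** agree under every section. The conflict is confined to rows 2 and 3.
2. **Does the word mild in the 2.9.4 severity field settle the scope?** No. A mild event can still receive medical attention (row 1), so the field is compatible with either scope. It leans towards the broad one without establishing it.
3. **Could 2.9.3 set the scope while 2.9.4 only lists the fields?** Possibly. But the opening of 2.9 is not a list of fields, and its recording clause carries the same qualifier. No sentence says which section prevails.
4. **Is the gap in detection or in recording?** In recording. Both 2.9 and 2.9.3 provide for monitoring throughout the study. Controls are also observed for 4 hours after dosing before they may leave the research center on Days 1 and 2, and for 4 hours after catheter removal.
5. **How exposed is row 3?** Less than row 2. Section 2.5.5.8 repeats the baseline laboratory tests at exit in both groups, apart from the pregnancy test and drug screen. Abnormal results are followed to resolution unless the study physician judges this unnecessary. That is not the same as recording an adverse event, but the exit data exist and are reviewed however 2.9.4 is read.
6. **Serious adverse events.** By 2.3.1, study-group participants are inpatients for all study interventions. An event that only prolongs the stay therefore meets the hospitalization criterion of 2.9.5 but not that of 2.9.1. It may still qualify under 2.9.1 as an important medical event, and 2.9.5, which governs reporting, already has the fuller wording.

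**The case against.** The strongest reply is that recording a subset does not contradict recording the whole. Only 2.9.3 states a universal scope, neither 2.9 nor 2.9.4 contains a word such as only, and 2.9.4 lists mild among the grades. On this view the drafting is loose but the intended answer is clear. Much of this stands: the broad scope may well be what was meant, and the harm arises only if staff treat 2.9.4 as exclusive despite the sentence just before it. It does not remove the inconsistency. If the broad scope is intended, the qualifier in two places misleads. If the narrow one is intended, 2.9.3 is wrong. One side needs editing in either case.

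Three stronger readings are tempting, and the documents support none of them.

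- **A reader might infer that mild events will be missed and tolerability will be understated.** The text shows only that they can be left out by someone following 2.9.4 literally.
- **A reader might infer that the undefined threshold biases the comparison between inpatients and healthy volunteers.** It could be applied differently in the two groups, but nothing in the documents shows that it would be, and no comparison of adverse events is planned.
- **A reader might infer that serious events prolonging a hospital stay will go unreported.** Section 2.9.5 covers them expressly.

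**Conclusion.** The scope of adverse event recording is internally inconsistent, and the severity is minor. The conclusion that the sections differ rests on their wording alone. The consequence is conditional: if 2.9.4 is applied as worded, mild untreated symptoms can go unrecorded and the account of the sole secondary objective may be understated. The size of that understatement cannot be derived, because the documents give no expected event rates and plan no incidence analysis. The exposure is mainly to untreated symptoms, since exit laboratory abnormalities are collected and followed separately. The primary pharmacokinetic endpoints do not depend on adverse event records. The difference between the two serious adverse event definitions is real, but it is a matter of consistency with little practical risk.

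**What to change.** - **2.9.4:** change the subject of the opening sentence to *All adverse events, whether or not they require medical attention*. Leave the rest of the sentence and the list of fields unchanged.
- **2.9, opening paragraph:** split the sentence. Keep the clause on treatment by the study physician exactly as it is, and state separately that the investigator records every adverse event.
- **2.9.1 (minor consistency edit):** extend the hospitalization criterion in the serious adverse event definition to match 2.9.5, so that prolongation of a stay is included.

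No change is needed in 2.9.3, which already states the broad scope. The cost is three wording edits and some additional adverse event entries for 16 participants (10 patients + 6 volunteers). No visit, sample or assessment is added.
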